8.2 Sample Size Determination

Objective 1.1 – Compare the performance of the Xpert MTB/RIF Ultra assay between the GeneXpert and Omni systems with testing of clinical specimens

Table 1. Sample size required to assess percent agreement between platforms at a given confidence interval width with 95% confidence.

		Width of Confidence Interval						
		5%	7.5%	10%	12.5%	15%	17.5%	20%
	99%	61	28	16	10	7	5	4
	97.5%	150	67	38	24	17	13	10
	95%	292	130	73	47	33	24	19
	92.5%	427	190	107	69	48	35	27
	90%	554	246	139	89	62	46	35
	87.5%	673	299	169	108	75	55	43
SL	85%	784	349	196	126	88	64	49
tform	82.5%	888	395	222	142	99	73	56
% Agreement between platforms	80%	984	438	246	158	110	81	62
	77.5%	1072	477	268	172	120	88	67
	75%	1153	513	289	185	129	95	73
seme	72.5%	1226	545	307	197	137	101	77
Agre	70%	1291	574	323	207	144	106	81
%	67.5%	1349	600	338	216	150	111	85
	65%	1399	622	350	224	156	115	88
	62.5%	1441	641	361	231	161	118	91
	60%	1476	656	369	237	164	121	93
	57.5%	1503	668	376	241	167	123	94
	55%	1522	677	381	244	170	125	96
	52.5%	1533	682	384	246	171	126	96

Omni Bio-equivalency study Protocol # TB046-bioequiv1.0

385 246 171 126 97

The GeneXpert and Omni platforms are anticipated to demonstrate equivalent performance for the testing for Xpert Ultra cartridges. Given a confidence level of 95%, a sample size of 150 would yield a confidence interval of 5% to determine 97.5% agreement between platforms. Testing 160 MTB positive sample size would ensure these parameters are met even given a 6.25% error/invalid rate.

Objective 1.2 – Compare the performance of the Xpert MTB/RIF Ultra assay between the GeneXpert and Omni systems with testing of MMQCI controls at high temperature and humidity conditions

		Width of Confidence Interval						
		5%	7.5%	10%	12.5%	15%	17.5%	20%
	99%	43	20	11	7	5	4	3
	97.5%	106	47	27	17	12	9	7
	95%	206	92	52	33	23	17	13
	92.5%	301	134	76	49	34	25	19
rms	90%	390	174	98	63	44	32	25
% Agreement between platforms	87.5%	474	211	119	76	53	39	30
	85%	552	246	138	89	62	46	35
	82.5%	625	278	157	100	70	52	40
	80%	693	308	174	111	77	57	44
green	77.5%	755	336	189	121	84	62	48
% A{	75%	812	361	203	130	91	67	51
	72.5%	864	384	216	139	96	71	54
	70%	910	405	228	146	102	75	57
	67.5%	950	423	238	152	106	78	60
	65%	985	438	247	158	110	81	62

Table 2. Sample size required to assess percent agreement between platforms at a given confidence interval width with 90% confidence.

Omni Bio-equivalency study

Protocol # TB046-bioequiv1.0

	62.5%	1015	451	254	163	113	83	64
	60%	1039	462	260	167	116	85	65
	57.5%	1058	471	265	170	118	87	67
	55%	1072	477	268	172	120	88	67
	52.5%	1080	480	270	173	120	89	68
	50%	1083	481	271	174	121	89	68

Given a confidence level of 90%, a sample size of 120 would yield a confidence interval of 10% to determine 87.5% agreement between platforms, or a confidence interval of <5% to determine 97.5% agreement between platforms.

9 Regulatory and Ethical Considerations

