Study design	This is an external laboratory equivalency study to evaluate the performance Xpert MTB/RIF Ultra testing on Omni compared to GeneXpert. This study will use well-characterized clinical specimens from existing sample banks to assess the positive and negative concordance between the two devices at normal environmental conditions. The study will also evaluate the positive and negative concordance between the two devices at high heat and humidity using Cepheid controls, and look at differences in Tm and Ct values between platforms for Ultra testing of the same controls at 3x Ultra LoD.		

Omni Bio-equivalency study Protocol #

Study sites/setting	San Raffaele Scientific Institute, Milan, Italy	
Study population Clinical specimens selected from the FIND specimen bank and pro MMQCI controls		rovided
Sample Size	Sample SizeObjective 1.1: Xpert MTB/RIF Ultra testing of a total of 160 MTB positi and 40 MTB negative specimens on both Omni and GeneXpert	
	Objective 1.2: Xpert MTB/RIF Ultra testing of a total of 30 replicates of the MTB WT control and 30 replicates of the MTB MDR control at 3x the Ultra LoD per each environmental condition on Omni and at baseline conditions on GeneXpert	
	One negative control will also be tested per day per Omni/Gene Xpert device.	
Study duration5 months from conception to completion, 30 days of testing.		
Time schedule Study set up (IRB approval, study agreements) Shipment of devices, samples, Cepheid controls and cartridges Testing and data reporting Start Q2 2020		8 weeks 3 weeks 6 weeks

Schedule of Activities

Procedure	Timeline	Notes
Study set up (IRB approval, study agreements)	1 December – 15 July 2020	*Cepheid Omni delay has impacted timelines. No instruments available before July
Shipment of devices, samples, Cepheid controls and cartridges	16 July – 6 August 2020	*Additional time allocated for shipments given COVID-related delays
Testing and data reporting	7 August – 18 Sept 2020	

1 Introduction

The GeneXpert Omni system ('Omni') is a single-cartridge, battery-powered, point-of-care platform for rapid, onsite molecular tuberculosis testing at primary care clinics in high burden countries.

The study described herein is an external, laboratory study to investigate the equivalency of Xpert MTB/RIF Ultra testing on the Omni platform compared to the GeneXpert platform.

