1.3 Benefit/Risk Assessment

No participants will be recruited during this study and so no risks are expected. In contrast, the knowledge gained from this study will potentially benefit society by improving TB and drug resistance detection.

2 Study Objectives and Endpoints

The aim of the study is to assess whether Xpert MTB/RIF Ultra testing on the Omni platform is equivalent to Xpert MTB/RIF Ultra testing on the GeneXpert platform.

Objectives	Outcomes
Primary	
1.1 Compare the performance of the Xpert MTB/RIF Ultra assay between the GeneXpert and Omni systems with testing of clinical specimens	1.1 Positive and negative concordance of Xpert MTB/RIF Ultra testing on Omni compared to GeneXpert for clinical specimens
1.2 Compare the performance of the Xpert MTB/RIF Ultra assay between the GeneXpert and Omni systems with testing of MMQCI controls at high temperature and humidity conditions	1.2 Positive and negative concordance of Xpert MTB/RIF Ultra testing on Omni compared to GeneXpert for MMQCI controls at different temperature and humidity conditions
	1.3 Average difference in Ct-values for each Xpert MTB/RIF Ultra MTBC probe when testing on Omni compared to GeneXpert for MMQCI controls at different temperature and humidity conditions
	1.4 Average difference in Tm values for each Xpert MTB/RIF Ultra rpoB probe when testing on Omni compared to GeneXpert for MMQCI controls at different temperature and humidity conditions

3 Study Design

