6.1 Study workflow

[figure not shown]
The study flow is shown in Figure 1.

FIND will ship the required clinical specimens selected for this study to the investigational site. Cepheid will ship the platforms, cartridges, and MMQCI controls required for this study to the site.

For the equivalency assessment of Omni against GeneXpert at controlled environmental conditions, each clinical specimen will be prepared, homogenized and split into two equal aliquots for Xpert MTB/RIF Ultra testing. The two Xpert MTB/RIF Ultra cartridges will be randomized for testing, with one cartridge tested using the Omni platform and one cartridge tested using the GeneXpert platform at room temperature conditions.

For the equivalency assessment that is carried out at high environmental conditions, Xpert MTB/RIF Ultra cartridges will be stored at the respective temperature and humidity conditions for 72 hours prior to testing. Each environmental condition will be tested by Omni using 30 replicates of the wild type control and 30 replicates of the MDR control at 3x the Ultra LoD. GeneXpert testing using Xpert MTB/RIF Ultra will also be performed using 30 replicates of the wild type control and 30 replicates of the Ultra LoD. Four Omni systems will be used for testing at each environmental condition. Daily negative control testing will also be performed for each device.

Figure 1: Sample workflow

*30 replicates of each control will be tested by each platform at the listed conditions (i.e. 30 replicates per condition) at 3x LoD. Replicate testing will be divided between 4 Omni instruments. Daily negative control testing will also be performed for Omni and GeneXpert. **Ultra cartridges to be stored at respective condition (20-25C, 50% RH or 35C, 90% RH) for 72hr prior to testing

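### Section 8.2 gives the Objective 1.2 precision for 120 replicates, but the design has 60 per environmental condition and 30 per RIF call, so the intervals will be 1.4 to 2.0 times as wide

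*Protocol*

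**What the plan says.** Under Objective 1.2, section 8.2 presents Table 2, titled "Sample size required to assess percent agreement between platforms at a given confidence interval width with 90% confidence". The sentence after it reads "Given a confidence level of 90%, a sample size of 120 would yield a confidence interval of 10% to determine 87.5% agreement between platforms", and continues "or a confidence interval of <5% to determine 97.5% agreement between platforms". The section does not say how 120 arises or which comparison it serves.

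The replicate numbers are set elsewhere. Section 6.1: "Each environmental condition will be tested by Omni using 30 replicates of the wild type control and 30 replicates of the MDR control". The Sample Size row of the synopsis gives the same wild-type number and "30 replicates of the MTB MDR control at 3x the Ultra LoD per each environmental condition on Omni and at baseline conditions on GeneXpert". Section 4 repeats 30 and 30 for each condition.

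The endpoint in section 2 is "1.2 Positive and negative concordance of Xpert MTB/RIF Ultra testing on Omni compared to GeneXpert for MMQCI controls at different temperature and humidity conditions". The analysis table in section 8.1 counts MTB detection, RIF-resistant calls and RIF-sensitive calls in separate rows. It does so for Omni across conditions, and for Omni against GeneXpert at normal conditions. Section 8.1 also says that no detailed SAP will be written, so section 8.2 is the only statement of precision for this objective.

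**The concern.** Performance under heat and humidity is a primary objective. It can be judged only by looking at each condition separately. A reader of section 8.2 would expect a 90% interval about 10 points wide at 87.5% agreement, or under 5 points at 97.5%. If each condition has half of the 120 observations, and each RIF call a quarter, the reported intervals will be clearly wider than that. The reader would then credit the stress comparison with more precision than the design can give.

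**Working it through.** **Inputs.** Confidence level 90%, two-sided, z = 1.645 (section 8.2). Agreement of 87.5% and 97.5% (section 8.2). Replicates per condition on Omni: 30 wild-type + 30 MDR = 60 (synopsis, sections 4 and 6.1). RIF-resistant calls can come only from the MDR control and RIF-sensitive calls only from the wild-type control, so 30 each per condition (section 8.1 with section 6.1).

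**Step 1: reproduce the plan's figures.** Table 2 follows the Wald formula for one proportion, `n = z² p(1−p) / (w/2)²`, where w is the full width.

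- p = 0.875, w = 0.10: n = 118.4, rounded up to 119 (Table 2: 119).
- p = 0.975, w = 0.05: n = 105.5, rounded up to 106 (Table 2: 106).

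Solved for the width, `w = 2z √(p(1−p)/n)`. At n = 120:

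- p = 0.875: 2 × 1.645 × √(0.109375/120) = 9.93%.
- p = 0.975: 2 × 1.645 × √(0.024375/120) = 4.69%.

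Both statements are correct for n = 120.

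**Step 2: where 120 could come from.** Two sums give it: 60 Omni replicates × the two conditions named in the footnote to Figure 1, or 60 Omni + 60 GeneXpert runs. The protocol states neither. The first averages over the factor that Objective 1.2 is meant to examine. The second does not give 120 agreement observations: it gives at most 60 pairs, or two groups of 60. Daily negative controls add nothing to the positive-control or RIF-call denominators.

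**Step 3: the same formula with the design's numbers (full 90% width).**

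| n | Use | At 87.5% | At 97.5% | Ratio to n = 120 |
|---|---|---|---|---|
| 120 | as stated | 9.9% | 4.7% | 1 |
| 60 | MTB detection, per condition | 14.0% | 6.6% | √(120/60) = 1.41 |
| 30 | each RIF call, per condition | 19.9% | 9.4% | √(120/30) = 2.00 |

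Table 2 shows much the same without calculation. At 87.5%, a 15% width needs 53 and a 20% width needs 30. At 97.5%, a 7.5% width needs 47 and a 10% width needs 27.

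**Step 4: agreement at which the stated widths would be met.** With 60 replicates, a 10% width needs agreement of about 94.1% or more, and a 5% width about 98.6% or more. With 30 replicates these become about 97.1% and 99.3%.

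**The case against.** Section 8.2 never says that 120 is per condition. With two conditions named, 60 × 2 = 120 is the number of Omni positive-control runs, and read as that total the sentence is true. This stands as far as it goes: nothing is miscalculated, and a reader who infers an arithmetic error would be wrong. It rescues only a pooled figure, though, and neither the endpoint nor the analysis table reports one.

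A second objection is that the platforms are expected to perform equivalently and the controls are run at three times the LoD, so 87.5% is not the likely result. If all 60 replicates are correct, the 90% Clopper-Pearson interval is 95.1% to 100%, a width of 4.9%. That is fair for MTB detection. For a RIF call, 30 of 30 gives 90.5% to 100%, a width of 9.5%. In any case, the protocol states its widths at 87.5% and 97.5%.

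Three stronger readings are tempting and are not supported:

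- **The intervals are nearly three times as wide as stated.** That ratio (28.1/9.9 = 2.8) appears only if percent agreement is replaced by a difference between two independent groups of 30. Section 8.2 does not claim to estimate that difference.
- **Percent agreement must be dropped for the controls.** The protocol gives no rule pairing an Omni replicate with a GeneXpert replicate, so agreement between platforms is loose wording here. But the controls have known expected results (Appendix 2) and section 8.1 counts correct calls, so a one-sample proportion is a legitimate summary. Dropping agreement would also reach into the wording of the primary endpoint.
- **An equivalence conclusion fails.** Objective 1.2 has no margin, acceptance threshold or test that uses the width.

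**Conclusion.** The stated sample size and the design are inconsistent. The n = 120 widths do not apply to the comparisons planned for Objective 1.2. On the protocol's own formula, the widths at 87.5% and 97.5% agreement are 14.0% and 6.6% for MTB detection per condition, and 19.9% and 9.4% for each RIF call per condition.

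This rests on reading the endpoint as reported by condition, which sections 2 and 8.1 support, and on no pooled analysis being intended. If pooling over two conditions was intended, the stated widths hold for that pooled figure alone. Figure 1 is not shown, so the number of conditions is known only from its footnote. The count of 60 per condition is fixed in the text and does not depend on the figure.

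This should be fixed. It is not critical, because no planned decision depends on the number.

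**What to change.** Replace the n = 120 sentence in section 8.2 with the precision for the planned comparisons, for example:

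> With 90% confidence and the formula behind Table 2, MTB detection in each environmental condition (60 replicates) has a full interval width of 14.0% at 87.5% agreement and 6.6% at 97.5%. Each RIF call in each condition (30 replicates) has a width of 19.9% and 9.4%.

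Alternatively, keep 120, say which runs are pooled to reach it, and justify that pooling for an objective about environmental conditions.

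Optionally, because control replicates are not paired between platforms, add the precision for a difference in detection proportions, from `w = 2z √(2p(1−p)/n)`. For 60 v 60 the widths are 19.9% at 87.5% and 9.4% at 97.5%. For 30 v 30 they are 28.1% and 13.3%.

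The main fix costs one reworded sentence and a less favourable stated precision. It adds no replicates and leaves the endpoint unchanged.

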9.1 Regulatory and Ethics Approvals

No human subjects will be enrolled for this study, and so no ethical issues are expected. The specimens used for this study were obtained from tuberculosis patients who authorized use of their material. To ensure confidentiality, the patient names will not be disclosed in any document.

Any amendments to the protocol must be approved prior to their implementation. The study will not start before the signature of the clinical study protocol of each contractual party involved has been obtained.

Clinical specimens and strains will be shipped to sites in adherence to international transport regulations and safety standards. Handling and manipulation of M. tuberculosis strains will be performed in an adequate biosafety laboratory (BSL-3) to minimize risk of contamination for the technical personnel and the environment. Given the nature of the study, termination due to safety or other reasons is not anticipated. In parallel, knowledge gained from this study may benefit society by improving TB and drug resistance diagnosis.

9.2 Financial Disclosure

Investigators and sub-investigators will provide FIND with sufficient, accurate financial information as requested to allow FIND to submit complete and accurate financial certification or disclosure statements to the appropriate regulatory authorities.

10 Data Handling and Record Keeping

FIND is responsible for the data management of this trial including quality control checks of the data and assessment of overall protocol compliance. Data will be exported from the Omni and Gene Xpert instruments and converted by FIND into a format applicable to the statistical software that will be used for the statistical analysis.

The investigator must permit study-related monitoring, audits, IRB/IEC review, and regulatory agency inspections and provide direct access to source data documents.

FIND or designee is responsible for the data management of this study including quality checking of the data.

Records and documents, pertaining to the conduct of this study must be retained by the investigator for at least 5 years after study completion unless local regulations or institutional policies require a longer retention period. No records may be destroyed during the retention period without the written approval of FIND. No records may be transferred to another location or party without written notification to FIND.

10.1 Source Data and Source Documents

Source documents provide evidence for the existence of the data and substantiate the integrity of the data collected. Source documents are filed at the investigator's site. For this study the source documents will be the results generated by the Omni and Gene Xpert instruments.

10.2 Data Management

Data Management procedures at FIND, including the setup of the database, programming edit and range checks and querying, are described in the Data Management Plan.

Test results from the Omni and Gene Xpert devices will be exported from the investigational device and electronic files will be transferred to FIND for further analysis. FIND will setup a secure data transfer system such as a File Transfer Protocol (FTP) server. Details will be provided in the Trial Manual.

No information concerning the trial or the data generated from the trial will be released to any unauthorized third party without prior written approval of FIND.

The study monitor or other authorized representatives of FIND or regulatory agencies may inspect all documents and records required to be maintained by the co-investigators.

Additional details relating to data entry procedures and timelines will be provided to the investigational site in the Data Management Plan.

11 Quality Management

Quality Management for this study consists of Quality Control activities, training and capacity building provided by FIND (or designee) to the investigational sites and laboratories, as well as the use of Standard Operating Procedures, Work Instructions, Tools and Templates.

Training on the protocol, will be provided by FIND and training on the different assays will be provided by the manufacturers, if this step has not been part of an earlier program. A Study Manual which describes all of the sample testing procedures will be provided by FIND prior to the commencement of the study.

Any missing data or data anomalies will be communicated to the site for clarification and resolution. The site will provide direct access to all study-related records, source data/documents, and reports for the purpose of monitoring and auditing by FIND and inspection by local and regulatory authorities, if requested.

11.1 Quality Control (monitoring)

Quality control should be applied to each stage of data handling to ensure that all data are reliable and have been processed correctly. The investigational site is responsible for performing regular Quality Control checks on the data they generate.

FIND will perform risk-based monitoring of this trial, and associated Quality Control checks, as described in the Monitoring Plan. Quality Assurance (auditing)

As part of routine Quality Assurance, FIND or designee may conduct an audit of the investigational site.

11.2 Trial and Site Closure

FIND designee reserves the right to close the study site or terminate the study at any time for any reason at the sole discretion of FIND. Study sites will be closed upon study completion. A study site is considered closed when all required documents and study supplies have been collected and a study-site closure visit has been performed.

The investigator may initiate study-site closure at any time, provided there is reasonable cause and sufficient notice is given in advance of the intended termination.

Reasons for the early closure of a study site by FIND or investigator may include but are not limited to:

- Failure of the investigator to comply with the protocol or local health authorities, FIND's procedures, including the failure to meet capacity requirements outlined at the start of the study.
- Discontinuation of further study intervention development

12 Publication Policy

Authorship for scientific publication of the trial results will be determined by mutual agreement and in line with International Committee of Medical Journal Editors authorship requirements, as described in the publication policy section of the contractual agreement.

Study results will be presented at international scientific conferences, published in international peer-reviewed journals and presented to WHO for review. Reporting will be in accordance to STARD guidelines.

13 References

- 1. WHO. Global TB Report 2019.; 2019.

Appendix 1: Protocol Amendment Summary Table Appendix 2: Package Insert for MMQCI Controls

Appendix 1: Protocol Amendment Summary Table

The Protocol Amendment Summary of Changes Table for the current amendment is located directly before the Abbreviations section.

Amendment [amendment number]: ([date])

Overall Rationale for the Amendment

Section # and Name	Description of Change	Brief Rationale		

Appendix 2: Package Insert for MMQCI Controls

Research Use Only Maine Molecular Quality Controls, Inc.

[name] [contact], [contact] Web: www.mmqci.com, Email: [contact]

INTROL® TB PANEL M114plus **INSTRUCTIONS FOR USE**

INTENDED USE:

INTROL® TB Panel M114plus is intended for use as a quality control to monitor the nucleic acid detection of *M. tuberculosis* (MTB) and the mutations associated with multi-drug resistant MTB (MDR-TB) on the GeneXpert[#] System

The World Health Organization (WHO) reports that about 1.7 billion people, 23% of the world's population, are estimated to have a latent TB infection, and are thus at risk of developing active TB disease during their lifetime.¹ There has been major progress in subsequent years - more than 60 million people have been documented as treated and cured since 2000, and case and death rates have fallen steadily. Nevertheless, worldwide, around 10 million people still fall ill with the disease each year (more adults than children, and more men than women), and TB is one of the top 10 causes of death. It is also the leading cause of death from a single infectious agent, ranking above HIV/AIDS.²

INTROL® TB Panel M114plus is provided for Research Use Only (RUO). It cannot be cloned, sold, or transferred without the explicit written consent of MMQCI

PRODUCT SUMMARY and PRINCIPLE:

INTROL® TB Panel M114plus is composed of 3 positive controls and 1 negative control. The positive controls consist of non-infectious, synthetic MTB DNA encapsulated in bacterial cells. The MTB DNA does not include the entire MTB genome. MTB gene segments present among the positive controls are: IS6110, IS1081, hsp65, 16S rRNA, 23S rRNA, inhA, katG, and rpoB. Drug resistance mutations are incorporated in segments inhA, katG, and rpoB, as indicated in Table 1. Not all mutations listed are detected by Xpert MTB assays on the GeneXpert System. The negative control contains buffer and preservative only.

Best practice is to establish a quality control program for every assay performed by the laboratory.^{3,4} Routine use of quality controls that are consistent lot to lot and monitor the entire assay assists the laboratory in identifying shifts, trends, and increased frequency of random errors caused by variations in the test system, such as failing reagents and pipetting errors. Early investigation can prevent failed assay runs.

COMPOSITION:

INTROL® TB Panel M114*plus* is comprised of three bottles each of INTROL® TBWT-04, INTROL® TBMDR1-04, INTROL® TB1081MDR2, and INTROL® TBNEG, 1.0 mL each. INTROL® TBWT-04 and INTROL® TBMDR1-04 contain the following MTB gene segments: IS6110, hsp65, 16S rRNA, 23S rRNA, inhA, katG, and rpoB. INTROL® TB1081MDR2 contains MTB gene segments: IS1081, hsp65, 16S rRNA, 23S rRNA, inhA and rpoB. The MTB gene segments consist of non-infectious, synthetic MTB DNA encapsulated in chemically fixed and killed 1aboratory betrain cells supended in buffer and chemically fixed and killed laboratory bacterial cells suspended in buffer and preservatives. INTROL* TBNEG contains buffer and preservative only. The presence or absence of drug resistance mutations is specified for each bottle in Table 1.

Table 1. Drug Resistance Mutations* found in INTROL® TB Panel M114plus

Control	Drug Resistance Mutation
INTROL [®] TBWT-04	no mutations/ wildtype (H37Rv)
INTROL [®] TBMDR1-04	rpoB: F505L, L511P, D516V, H526Y
	inhA: -15
	katG: S315T (AGC> ACC)
INTROL [®] TB1081MDR2	rpoB: S522L, H526D, S531L inhA Mutant: -8T>C
INTROL [®] TBNEG	No MTB DNA, no cells

*References citing the mutations can be found at www.tbdreamdb.com

PRECAUTIONS AND WARNINGS:

INTROL® TB Panel M114plus has been tested on the GeneXpert® System only. It cannot be cloned, sold, or transferred without the explicit written consent of MMQCI. This product does not contain any biological material of human origin or infectious microorganisms. Do not freeze.

STORAGE and STABILITY:

Upon receipt and after opening, the material should be stored at $2^\circ-8^\circ C.\;$ Do not freeze.

Unopened controls are stable through the expiration date printed on each bottle when stored at $2^{\circ} - 8^{\circ}$ C. Opened material tightly capped and returned to the refrigerator ($2^{\circ} - 8^{\circ}$ C) shortly after use is stable for thirty (30) days from the date of opening.

INSTRUCTIONS FOR USE ON THE GeneXpert® System:

- Each bottle contains 1.0 mL of control material
- Allow controls to come to room temperature
- Throughly mix controls by vigorously inverting several times immediately before use.
- Before opening bottle, shake down or tap bottle on hard surface to be sure all liquid is out of cap. Add 2.0 mL Sample Reagent to each control vial.
- 5.
- Mix by inverting the vial 10 times.
- Let the vial sit at room temperature for 15 minutes. Invert several times 7 half way through incubation period as you would for a sputum sample. Open the Xpert[®] MTB/RIF cartridge lid and transfer 2.0 mL of respective 8
- Sample Reagent treated control, using a sterile transfer pipette. Close lid.
- Transfer cartridge to the GeneXpert system.
 Scan cartridge, enter sample ID and start the run.

LIMITATIONS:

INTROL[®] TB Panel M114*plus* is designed for use with MTB amplification assays that target one or more of the following MTB gene segments: IS6110, IS1081, hsp65, 16S rRNA, 23S rRNA, inhA, katG, and rpoB. Only those segments are present in INTROL[®] TB Panel M114*plus*.

EXPECTED VALUES:

Gentral	Xpert MTB/RIF		
Control	Expected result		
INTROL [®] TBWT-04	MTB DETECTED		
	Rif Resistance NOT Detected		
INTROL [®] TBMDR1-04	MTB DETECTED		
	Rif Resistance DETECTED		
INTROL [®] TB1081MDR2	MTB DETECTED		
INTROL IBI081MDR2	Rif Resistance DETECTED		
INTROL [®] TBNEG	MTB NOT DETECTED		

REFERENCES

- WHO report 2018:
- https://www.who.int/tb/publications/global_report/en/
- "Ten Facts About Tuberculosis," WHO, September 2018:
- http://www.who.int/features/factfiles/tuberculosis/en/index.html ISO 15189: Medical laboratories - Particular requirements for quality and 3.
- competence. CAP Molecular Pathology Checklist; Commission on Laboratory 4. Accreditation, Laboratory Accreditation Program, Mol.20000

ORDERING INFORMATION:

INTROL® TB Panel M114plus

Part Number: M114plus Kit Contains:

12 bottles x 1.0mL 3 each TBWT-04, TBMDR1-04, TB1082MDR2, & TBNEG

M114plus 092319.000

Omni Bio-equivalency study

Protocol # TB046-bioequiv1.0
